4.10 Clinical studies

4.10.1 Clinical studies of p24CE1/2 pDNA

This is a first-in-human study for the p24CE1/2 pDNA vaccine.

4.10.2 Clinical studies of p55^{gag} pDNA

DAIDS has developed significant clinical experience with pDNAs that contain *gag* inserts (multiple variants), including the use of intramuscular administration with electroporation to deliver a *gag* pDNA with *IL-12* pDNA. These trials include: HVTN 060, 063, 070, 080 and 087.

4.10.3 Clinical studies of HIV-1 DNA vaccines given with GENEVAX® IL-12 pDNA adjuvant IM with Electroporation

Table 4-2 Summary of clinical studies of HIV-1 DNA vaccines with GENEVAX® IL-12 DNA plasmid and EP in healthy HIV-uninfected adults

Study number/ clinicaltrials.gov identifier	Study population	Test article(s)	Trial design / route of delivery/ schedule / N (vaccinee/placebos)
HVTN 080/ NCT00991354	HIV- uninfected	- PENNVAX®- B pDNA	Grp 1: 3 mg PV-B alone, IM/EP, month 0, 1, 3 N = 10/2
	healthy adults	GENEVAX® IL-12 pDNA	Grp 2: 3 mg PV-B + 1 mg IL-12 pDNA, IM/EP, month 0, 1, 3 N = $10/2$
			Grp 3: 3 mg PV-B + 1 mg IL-12 pDNA, IM/EP, month 0, 1, 3 N = 20/4
IAVI study	HIV-	- HIV-MAG	Grp 1: 3 mg HIV-MAG pDNA, IM/EP, month 0, 1, 2
B004/ NCT01496989	uninfected healthy	pDNA + GENEVAX®	2×10^{10} vp Ad35 GRIN/ENV, IM, month 6 N = 12/3
	adults	IL-12 pDNA - Ad35 GRIN/ENV	Grp 2: 3 mg HIV-MAG + 0.1 mg IL-12 pDNA, IM/EP, month 0, 1, 2 2×10^{10} vp Ad35 GRIN/ENV, IM, month 6 N = 12/3
			Grp 3: 3 mg HIV-MAG + 1 mg IL-12 pDNA, IM/EP, month 0, 1, 2 2 × 10 ¹⁰ vp Ad35 GRIN/ENV, IM, month 6 N = $12/3$
			Grp 4: 3 mg HIV-MAG + 1 mg IL-12 pDNA, IM/EP, month 0 2×10^{10} vp Ad35 GRIN/ENV, IM, month 4 N = 12/3
			Grp 5: 2×10^{10} vp Ad35 GRIN/ENV, IM, month 0 3 mg HIV-MAG + 1 mg IL-12 pDNA, IM/EP, month 6
			N = 12/3
HVTN 087/ NCT01578889	HIV- uninfected healthy	- HIV-MAG pDNA + GENEVAX®	Grp 1: 3 mg HIV-MAG pDNA alone, IM/EP, month 0, 1, 3 1×10^8 PFU rVSV HIV gag, IM, month 6 N = 22/3
	adults	IL-12 pDNA - rVSV HIV gag	Grp 2: 3 mg HIV-MAG + 0.25 mg IL-12 pDNA, IM/EP, month 0, 1, 3 1×10^8 PFU rVSV HIV gag , IM, month 6 N = 22/3
			Grp 3: 3 mg HIV-MAG + 1 mg IL-12 pDNA, IM/EP, month 0, 1, 3 1×10^8 PFU rVSV HIV gag , IM, month 6 N = 22/3
			Grp 4: 3 mg HIV-MAG + 1.5 mg IL-12 pDNA, IM/EP, month 0, 1, 3 1×10^8 PFU rVSV HIV gag , IM, month 6 N = 22/3

In HVTN 080, healthy HIV-uninfected volunteers received 3 mg PENNVAX[®]-B (*gag, pol, env*) with or without 1 mg *IL-12* pDNA by IM injection followed by in vivo EP (IM/EP) (CELLECTRA[®] EP system) at a single injection site. In this study, adjuvant activity was seen with *IL-12* pDNA. While the difference was not statistically significant, in HVTN 080 the proportion of volunteers making a vaccine-specific CMI response was almost 2-fold greater in the group that received Profectus' GENEVAX[®] IL-12 pDNA adjuvant given with EP compared to the small group receiving no *IL-12* pDNA (see Figure 4-16, Figure 4-17).

[figure not shown]

Figure 4-16 HIV-specific CD4+ T cell ICS responses in HVTN 080

[figure not shown]

Figure 4-17 HIV-specific CD8+ T-cell ICS responses in HVTN 080

In HVTN 087, several dose levels of *IL-12* pDNA (GENEVAX[®] IL-12 DNA plasmid) were tested for adjuvant activity, with HIV-MAG (HIV-1 *gag/pol* and HIV-1 *nef/tat/vif, env*) pDNA vaccine delivered IM/EP with the Ichor TDS-IM EP Device. In HVTN 087 the healthy HIV-uninfected volunteers received the HIV-MAG pDNA vaccine given with 0, 0.25, 1 and 1.5 mg *IL-12* pDNA IM/EP divided equally across two injection sites. The HIV-MAG pDNA vaccinations were followed by a VSV HIV *gag* boost. The results of

HVTN 087 with regards to the adjuvant activity of *IL-12* pDNA suggest that the highest dose of *IL-12* pDNA was associated with an increased magnitude of CD8+ T-cell responses following the VSV HIV *gag* boost, compared with group 1, which did not receive *IL-12* pDNA (p = 0.0185, Figure 4-19). The ability to see statistically significant differences between the study arms was limited by the small sample sizes.

[figure not shown]

Figure 4-18 HIV-specific CD4+ T-cell ICS responses in HVTN 087

[figure not shown]

Figure 4-19 HIV-specific CD8+ T-cell ICS responses in HVTN 087

However, the highest CD4+ T-cell response rate to DNA vaccination (pre-VSV boost) was seen in group 1, without *IL-12* pDNA (Figure 4-18). Given the ability of IL-12 to shift vaccine-specific immunity toward a Th1 response, *IL-12* pDNA as an adjuvant could contribute to CD8+ cellular immune responses to the p24CE1/2 pDNA vaccine.

IAVI has presented results of its B004 study, which also tested multiple injections of HIV-MAG and GENEVAX[®] *IL-12-*4532 DNA IM/EP (Ichor TDS-IM EP Device) in healthy volunteers [7]. The study tested the groups shown in Table 4-3. The vaccine regimens tested were adequately safe with no SAEs or AEs that were probably or definitely related to vaccine. The vaccine regimens in the 3 study groups shown were similarly rated with respect to tolerability.

With respect to cellular responses assessed by IFN- γ ELISpot, at baseline there were no responders. After the 3 pDNA priming injections, response rates among vaccinees were 82% (9/11) in Group 1, 64% (7/11) in Group 2, and 42% (5/12) in Group 3. After the Ad35-GRIN/ENV boost, response rates among vaccinees were 73% (8/11) in Group 1, 82% (9/11) in Group 2, and 89% (8/9) in Group 3. Samples from 8 participants in each group were also assessed with 7-color ICS to assess expression of IL-2, TNF- α , and IFN- γ in response to peptides matched to the HIV-MAG vaccine. Groups 1-3 had similar CD4+ and CD8+ T-cell response rates and magnitudes, and the polyfunctionality profiles were similar. An ELISA assay for HIV-specific antibodies to Env A and Env B (matched to the HIV-MAG vaccine) and p24^{Gag} did not detect any HIV-specific antibodies following the DNA primes in any group. In summary, the vaccine regimens tested were immunogenic, but there was no clear indication of enhancement of immunogenicity of HIV-MAG by IL-12 DNA in this small trial. One shortcoming of this data is that the participants were not all evaluated for CD8+ responses with ICS. It is not clear how the specific participant samples were selected for ICS assay, or how responses would have differed if measured by the HVTN laboratory assays.

Study arm	Ν	Month (Week)	Month (Week)	Month (Week)	Month (Week)
	1	0 (0)	1 (4)	2 (8)	6 (24)
	12	HIV-MAG	HIV-MAG	HIV-MAG	Ad35-GRIN/ENV
Group 1	3	Placebo	Placebo	Placebo	Placebo
Group 2	12	HIV-MAG+ IL-12 pDNA 0.1 mg	HIV-MAG+ IL-12 pDNA 0.1 mg	HIV-MAG+ IL-12 pDNA 0.1 mg	Ad35-GRIN/ENV
	3	Placebo	Placebo	Placebo	Placebo
Group 3	12	HIV-MAG+ IL-12 pDNA 1 mg	HIV-MAG+ IL-12 pDNA 1 mg	HIV-MAG+ IL-12 pDNA 1 mg	Ad35-GRIN/ENV
	3	Placebo	Placebo	Placebo	Placebo

Table 4-3 B004 schema

Note: HIV-MAG 3 mg delivered IM by EP. GENEVAX[®] IL-12 DNA plasmid co-administered with HIV-MAG delivered IM by EP. Ad35-GRIN/ENV 2×10¹⁰ vp delivered IM by standard needle injection.

The HVTN is also evaluating PENNVAX®-GP (Gag, Pol, Env) pDNA Vaccine and *IL-12* plasmid (INO-9012, Inovio Pharmaceuticals, Inc. Plymouth Meeting, Pennsylvania, USA), delivered via intradermal or IM/EP (CELLECTRA® EP system) in HVTN 098 (BB IND #16398, held by DAIDS). In that study, for IM delivery, the dose of PENNVAX®-GP is 8 mg and the dose of the Inovio *IL-12* plasmid is 1 mg, at a single injection site. The study is ongoing. No SAEs related to vaccination have been reported. Injection site pruritus has been reported by 19.1% of participants and presyncope following the vaccination procedure in 5.3%. Another *IL-12* pDNA (pUMVC3-hIL-12-NGVL3, City of Hope Center for Biomedicine and Genetics, Duarte, CA) has been given in doses up to 5.8 mg per administration delivered with EP directly into melanoma tumors, with no dose limiting systemic toxicities noted [91]. Hence, we do not anticipate any significant systemic or local adverse effects related to the use of *IL-12* pDNA IM with EP at the proposed dose.

Taken together, the studies suggest that *IL-12* pDNA delivered with plasmid DNA vaccines with EP may have a dose-dependent adjuvant effect on CD8+ responses. *IL-12* pDNA has been given at doses up to 1 mg at a single injection site with IM/EP and up to 1.5 mg total IM/EP at one visit (2 injection sites). Given the focus of this study on evaluating cellular immune responses, *IL-12* pDNA may provide an advantage to the evaluation of immunogenicity of the p24CE and p55^{gag} pDNA vaccines.

4.11 Potential risks of study products and administration

Common	• Mild transient cutaneous bleeding, bruising/ecchymosis				
	• Mild to moderate injection site pain, tenderness, pruritus, erythema, or swelling/induration/edema				
	 Malaise/fatigue, myalgia, or headache in the first few days following injection 				
Less common	Severe injection site pain or tenderness				
	• Transient paresthesia or hypoesthesia in the injected limb				
	• Fever, chills, flu-like syndrome, arthralgia, rash, nausea, or dizziness in the first few days following injection				
	 Vasovagal reaction/lightheadedness/dizziness related to the injection procedure 				
	Transient changes in clinical laboratory values				
	• Injection site hematoma, laceration, bruising/ecchymosis, other transient lesions, itching, or bleeding related to the injection procedure				
	• A vaccine-induced positive HIV antibody test result				
Uncommon or rare	• Severe localized injection site reaction, such as sterile abscess or secondary bacterial infection				
	 Allergic reaction, including rash, urticaria, angioedema, bronchospasm, or anaphylaxis 				
	Muscle damage at the injection site				
	• Injection needle contact with the bone				
	Difficulty removing EP device				
	• Syncope				
Theoretical risks	Autoimmune disease or cancer				
	• Electrical injury with EP				
	• Disruption of function of implanted electronic medical devices with EP				
	• Exacerbation of cardiac arrhythmias with EP				
	• Effects on a participant's response to an approved HIV vaccine administered in the future				
	• Effects on susceptibility to HIV, if the participant is exposed to HIV				
	• Effects on the course of HIV infection/disease, if the participant is infected with HIV				
	• Effects on the fetus and on pregnancy				

Table 4-4 Summary of potential risks of study products and administration

5 Objectives and endpoints

5.1 Primary objectives and endpoints

Primary objective 1:

To evaluate the safety and tolerability of the HIV-1 pDNA vaccines p24CE1/2 and $p55^{gag}$ administered with *IL-12* pDNA by intramuscular injection with electroporation

Primary endpoints 1:

- Frequency and severity of local injection/EP site and systemic reactogenicity signs and symptoms
- Frequency of AEs categorized by MedDRA body system, MedDRA preferred term, severity and assessed relationship to study products. Detailed description of all AEs meeting DAIDS criteria for expedited reporting
- The distribution of values of safety laboratory measures at baseline and at follow-up visits post vaccination
- Number of participants with early discontinuation of vaccinations and reason for discontinuation
- Magnitude of local injection/EP site pain as measured by a visual analog scale
- Distribution of responses to questions regarding acceptability of study injection procedures

Primary objective 2:

To compare the two pDNA prime/boost strategies with respect to breadth (defined as the number of targeted CEs) of $CD4^+$ and $CD8^+$ T-cell responses to conserved regions of the $p24^{Gag}$ protein

Primary endpoint 2:

The number of targeted CEs by CD4⁺ and CD8⁺ T-cell responses measured by ICS 2 weeks after the second and fourth vaccinations

5.2 Secondary objectives and endpoints

Secondary objective 1:

To determine the effect of the different prime/boost regimens on the magnitude and polyfunctionality of T-cell responses induced by the different priming vaccinations

Secondary endpoint 1:

Rate, magnitude and polyfunctionality of CD4⁺ and CD8⁺ T-cell responses measured by ICS to p24CE and HIV Gag, 2 weeks after the second and fourth vaccinations

Secondary objective 2:

To determine the effect of the different prime/boost regimens on the specificity of T-cell responses induced by the different primes

Secondary endpoint 2:

Epitope specificity of T-cell responses measured by IFN- γ ELISpot to p24CE and HIV Gag, 2 weeks after the second and fourth vaccinations

Secondary objective 3:

To evaluate the humoral immunogenicity of the HIV-1 pDNA vaccines p24CE1/2 and $p55^{gag}$ administered alone, in combination, or sequentially by intramuscular injection with electroporation

Secondary endpoint 3:

Rate and magnitude of humoral immune responses to Gag measured 2 weeks after the 4th vaccination by binding antibody multiplex assay

Secondary objective 4:

To determine the frequency of circulating Tfh in response to each vaccination regimen

Secondary endpoint 4:

Rate and magnitude of CD4⁺ cTfh measured by ICS

5.3 Exploratory objectives

Exploratory objective 1:

To further evaluate immunogenicity of the different vaccine regimens, additional immunogenicity assays may be performed, including on samples from other time points, based on the HVTN Laboratory Assay Algorithm

Exploratory objective 2:

To determine the frequency of plasmablasts in response to each vaccination regimen

Exploratory objective 3:

To evaluate the breadth of the T cell receptor repertoire induced after pDNA vaccination by electroporation

Exploratory objective 4:

To conduct analyses related to furthering the understanding of HIV, immunology, vaccines, and clinical trial conduct

6 Statistical considerations

6.1 Accrual and sample size calculations

Recruitment will target enrolling 56 healthy, HIV-uninfected adult participants, aged 18 to 50 years.

To ensure that both men and women will be adequately represented in the trial, the trial will enroll at least approximately 40% of each sex overall. Hence, when approximately 33 participants of one sex are enrolled, recruitment of persons born of that sex will stop.

Since enrollment is concurrent with receiving the first study vaccination, all participants will provide some safety data. However, for immunogenicity analyses, it is possible that data may be missing for various reasons, such as participants terminating from the study early, problems in shipping specimens, low cell viability of processed peripheral blood mononuclear cells (PBMCs) or high background. Immunogenicity data from 17 phase 1 and 2 phase 2a HVTN vaccine trials, which began enrolling after June 2005 (data as of September 2014), indicate that 17% is a reasonable estimate for the rate of missing data at day 182. For this reason, the sample size calculations in Section 6.1.2 account for 4 enrolled participants receiving vaccine having missing data for each study arm at the primary immunogenicity endpoint.

6.1.1 Sample size calculations for safety

The goal of the safety evaluation for this study is to identify safety concerns associated with product administration. Sample size calculations for safety are expressed in terms of the ability to detect AEs requiring expedited reporting to DAIDS.

The ability of the study to detect serious adverse events (SAEs) can be expressed by the true event rate above which at least 1 SAE would likely be observed and the true event rate below which no events would likely be observed. Specifically, for each vaccine arm of the study (n =25), there is a 90% chance of observing at least 1 event if the true rate of such an event is 8.8% or more; and there is a 90% chance of observing no events if the true rate is 0.4% or less. As a reference, in HVTN vaccine trials from December 2000 through September 2010, about 4% of participants who received placebos experienced an SAE.

Probabilities of observing 0, 1 or more, and 2 or more events among arms of size 25 are presented in Table 6-1 for a range of possible true adverse event rates. These calculations provide a more complete picture of the sensitivity of this study design to identify potential safety problems with the vaccine.

True event rate (%)	Pr(0/25)	Pr(1+/25)	Pr(2+/25)
1	77.8	22.2	2.6
4	36	64	26.4
5	27.7	72.3	35.8
10	7.2	92.8	72.9
20	0.4	99.6	97.3
30	<0.1	>99.9	99.8
40	<0.1	>99.9	>99.9

Table 6-1 Probability of observing 0 events, 1 or more events, and 2 or more events, among arms of size 25, for different true event rates

An alternative way of describing the statistical properties of the study design is in terms of the 95% confidence interval for the true rate of an adverse event based on the observed data. Table 6-2 shows the 2-sided 95% confidence intervals for the probability of an event based on a particular observed rate. Calculations are done using the score test method [92]. For a given vaccine arm, if none of the 25 participants receiving a vaccine regimen experience a safety event, the 95% 2-sided upper confidence bound for the true rate of such events in the total vaccinated population is 13.3%.

 Table 6-2 Two-sided 95% confidence intervals based on observing a particular rate of safety endpoints for arms of size 25

Observed event rate	95% CI
0/25	[0.0, 13.3]
1/25	[0.2, 19.5]
2/25	[2.2, 25.0]

6.1.2 Sample size calculations for immunogenicity

For comparing the CD4+ and CD8+ T-cell endpoints between the 2 vaccine regimens, the primary analysis uses head-to-head superiority comparisons. The comparison will be performed separately for each of the primary breadth and secondary magnitude T-cell subset endpoints. No multiplicity adjustments are made for the multiple comparisons given the utility to favor higher power at the expense of a higher accepted false positive rate.

Figure 6-1 below summarizes power available for superiority testing. For these calculations, we assume 17% missing data (n=21 evaluable endpoints from each arm). Sample size calculations for breadth of response are based on data from the HVTN 083 trial and assume a beta-binomial distribution. Sample size calculations for ICS magnitude assume normally distributed magnitudes after natural log transformation with standard deviation = 1. The assumptions for the sample size calculations for ICS magnitude are based on the data from the HVTN 080 trial. Superiority test power is based on the Mann-Whitney U test with 2-sided p-value <0.05 as statistically significant.

If mean CE breadth in the vaccine recipients in Group 1 is 0.2 (0.5) then the study has 80% power to detect superiority in Group 2 if the true CE breadth the 2^{nd} group is at least 1.0 (1.5). A 2.5 fold-change in the vaccine recipients from Group 2 versus Group 1 is required to have 80% power to detect superiority in the T-cell response magnitude.

[figure not shown]

Figure 6-1 Power to detect superiority in CE Breadth and ICS Magnitude. Power calculations for the breadth of response were run under two different scenarios. In the first panel power the mean CE Breadth is assumed to be 0.2 for the vaccine recipients in Group 1 while the second panel assumes a mean CE Breadth of 0.5. In the third panel power calculations are shown for the magnitude of response. The x-axis in the first two panels is the CE Breadth for the vaccine recipients in Group 2 and for the third panel it the x-axis is the fold change in ICS response magnitude for vaccine recipients from Group 2 versus Group 1. Power curves are shown for N=20, 25, and 30 vaccine recipients per Group and account for 17% missing immunogenicity data.

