The focus of the study is a pDNA prime-boost vaccine regimen, comprising p24CE1/2 pDNA prime followed by $p24CE1/2 + p55^{gag}$ pDNA booster vaccination. This regimen focuses the priming response to highly conserved, but subdominant epitopes, which we hypothesize will then be boosted, and possibly broadened by a combination of p24CE1/2 vaccine, and full length *gag* in the booster vaccination. This strategy is expected to achieve significantly broader epitope recognition compared to a regimen of full-length *gag* pDNA vaccine given alone.

This trial will be composed of 2 groups receiving different prime-boost regimens. Group 1 will receive p24CE1/2 pDNA prime followed by co-delivery of p24CE1/2 pDNA and full-length *gag* pDNA (CE/CE+*gag*). Group 2 will receive prime and boost with the full-length *gag* pDNA (*gag/gag*). The vaccines will be co-administered with *IL-12* pDNA, and given with electroporation. Four vaccinations will be given in the series, with priming vaccinations at 0 and 1 month, and boost vaccinations given at 3 and 6 months. Cellular and humoral immune responses in vaccine recipients will be compared to a control set of individuals given placebo injections given with electroporation on the same schedule.

In summary, we hypothesize that by targeting regions of the HIV-1 p24^{Gag} protein that are invariable across Group M viruses, this vaccine approach may elicit specific immune responses linked to protection and viral control, rather than immune responses that may include decoy responses with detrimental effects or limited antiviral potential.

[figure not shown]

Figure 4-1 Alignment of p24CE1, p24CE2 and p24^{Gag} **proteins.** The schematic representation at the top of the figure shows the p55^{Gag} and its proteolytic processing products including p24^{Gag} protein. Below is the alignment of the amino acid (AA) sequences of the consensus p24^{Gag} sequences of different HIV-1 clades and of the seven CE encoded by the p24CE1/2 pDNA vaccine. The AA sequences of the p24^{Gag} of different HIV-1 clades (A, B, C), group M consensus, COT-M, and of the p24CE1 and p24CE2 proteins are shown. The CE1 to CE7 sequences with the single AA change per CE are indicated.

4.2 p24CE1/2 pDNA

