4.6.2 Prime-boost regimen

A prime-boost regimen of 4 vaccinations will be given, with injections at 0, 1 (priming immunogen) and 3, 6 months (booster immunogen(s)). This schedule allows for comparison with other HVTN studies of DNA vaccines given with IM/EP, which vaccinated participants on schedules of 0, 1 and 3 months or 0, 1, 3 and 6 months. Group 1 (CE/CE+gag) receives a combination of 2 immunogens for the boost. Group 2 (gag/gag) receives one immunogen as both the prime and the boost. Partially heterologous boost vaccinations are proposed in Group 1 to further increase the likelihood of robust immune responses.

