The breadth of the response, measured by the number of CE recognized per animal, was compared among groups which received different CE based vaccines [CE pDNA only (studies 2 and 3), CE/gag pDNA (studies 4 and 5) and CE/CE+gag pDNA (study 6) (Figure 4-11). The CE+gag pDNA booster vaccination induced responses with significantly increased breadth (2-6 CE per animal), compared to CE or CE/gag pDNA vaccines with 1-3 or 1-4 CE per animal (see above studies 4 and 5), with no difference among these groups. All CE based pDNA vaccines induced broader responses than the HIV p55^{gag} pDNA only vaccine, which induced responses to 0-2 CE per animal.

[figure not shown]

[figure not shown]
Figure 4-11 Increased breadth of the HIV CE-specific responses induced by a CE/CE+*gag***pDNA vaccine regimen.** A comparison of the CE breadth using different vaccine regimens is shown. For details see Table 4-1. The plot shows the number of CE recognized by each macaque immunized with HIV *gag* pDNA only (studies 10, 12, 13), HIV CE pDNA only (studies 2, 3, 6 using the priming data only), CE pDNA prime/*gag* pDNA booster vaccination (studies 4, 5) or CE pDNA prime/CE+*gag* pDNA booster vaccination (study 6). The total number of vaccinations and separately the number of vaccinations including p24CE pDNA are given. The median number of CE recognized, the range of CE responses, and the number of animals analyzed are indicated. P values are from an ANOVA (Dunnett's test). Peptide-stimulated samples were considered positive if the responses were 2-fold higher than that of the unstimulated medium only control and greater than 0.01 after subtracting the medium control value. Samples were acquired on a LSR II or Fortessa flow cytometer (BD Biosciences, San Jose, CA), and the data were analyzed using FlowJo software (Tree Star, Inc., Ashland, OR).

[figure not shown]
Priming with HIV p24CE pDNA is critical to induce immune responses to subdominant epitopes, and inclusion of the p24CE pDNA together with a plasmid expressing the full-length immunogen (study 6) as a boost is the most effective protocol to induce desirable responses with greatest breadth, magnitude and cytotoxic capability. Importantly, study 6 using HIV vaccine constructs recapitulated the SIV vaccine data (study 9). Hence, this vaccine regimen is proposed for the clinical trial.

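### Does the sample-size section power the trial for the wrong arm to win on CE breadth?

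*Protocol*

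**What the plan says.** **Who is in which group.** Protocol section 4.6.2 states "Group 1 (CE/CE+gag) receives a combination of 2 immunogens for the boost" and "Group 2 (gag/gag) receives one immunogen as both the prime and the boost". Section 4.1 and the schema agree with this, and SAP section 2.3 repeats the schema.

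**Which direction is expected.** Of the CE prime with CE-plus-gag boost, section 4.1 says "This strategy is expected to achieve significantly broader epitope recognition compared to a regimen of full-length" gag given alone. The macaque summary in section 4.9.3 points the same way: "All CE based pDNA vaccines induced broader responses than the HIV" gag-only vaccine.

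**What the power section says.** Section 6.1.2 begins "If mean CE breadth in the vaccine recipients in Group 1 is 0.2 (0.5") and goes on "then the study has 80% power to detect superiority in Group 2 if the true CE breadth" in that group is at least 1.0 (1.5). The magnitude sentence gives a 2.5-fold change as Group 2 over Group 1. The Figure 6-1 caption has the same orientation: "In the first panel power the mean CE Breadth is assumed to be 0.2 for the vaccine recipients in Group 1", with Group 2 on the horizontal axis.

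**How the comparison is tested.** Section 6.1.2 bases power on a Mann-Whitney U test, two-sided at 0.05, with 21 evaluable participants per arm. Primary objective 2 (section 5.1) is to compare the two strategies on breadth and names no expected winner. SAP section 8.4.1 makes all tests two-sided. The SAP has no sample-size section.

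**The concern.** Section 6.1.2 is the only power justification for primary objective 2. Read literally, it assumes that the investigational regimen elicits responses to well under one of seven CEs, and it gives the chance of showing that the comparator beats it. Section 4.1 argues the reverse. The orientation is the same in the breadth sentence, the magnitude sentence and the figure caption, so it cannot be dismissed as one mistyped digit.

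If power depended on which arm was higher, the trial would have no stated power for its own hypothesis, and 25 per arm would rest on the wrong scenario. A report that copied the text would also name the wrong arm as the one expected to be superior.

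**Working it through.** **Inputs from the documents**
- Vaccine recipients per arm: 25 (schema). Missing immunogenicity data: 17% (sections 6.1 and 6.1.2). 25 × 0.83 = 20.75, taken as 21.
- Test: Mann-Whitney U, two-sided 0.05 (section 6.1.2).
- Breadth: beta-binomial over 7 CEs (sections 6.1.2 and 4.2); means 0.2 vs 1.0 and 0.5 vs 1.5.
- Magnitude: natural-log scale, SD 1, ratio 2.5 (section 6.1.2).

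**Assumed, because the documents do not give it:** the beta-binomial dispersion, written as a within-participant correlation ρ and varied from 0 to 0.30.

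**Step 1: reproduce the plan's magnitude figure.** The difference is ln 2.5 = 0.916.
- Normal approximation: 0.916 / √(2/21) = 0.916 / 0.309 = 2.97; 2.97 − 1.96 = 1.01; power Φ(1.01) = 0.84.
- Multiplying n by the Mann-Whitney efficiency 3/π gives 0.83.
- Direct Mann-Whitney simulation (20,000 runs) gives 0.80, which is the plan's figure.

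**Step 2: does direction matter?** The two U statistics satisfy U₁ + U₂ = n₁n₂ = 21 × 21 = 441. The two-sided p-value depends only on the distance |U₁ − 220.5|. Exchanging the labels turns U₁ into 441 − U₁, which leaves that distance unchanged. Because the arms are equal in size, the scenario with Group 1 low and Group 2 high has exactly the same power as its mirror image. With unequal arms this would not hold exactly.

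**Step 3: confirm by simulation for breadth.** For mean m, set μ = m/7 and s = (1 − ρ)/ρ. Draw p from Beta(μs, (1 − μ)s), then breadth from Binomial(7, p); at ρ = 0, p = μ. There are 10,000 runs with tie correction. The exchanged columns use fresh draws.

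| ρ (assumed) | 0.2 vs 1.0, as written | exchanged | 0.5 vs 1.5, as written | exchanged |
|---|---|---|---|---|
| 0 | 0.940 | 0.938 | 0.930 | 0.930 |
| 0.05 | 0.896 | 0.897 | 0.867 | 0.855 |
| 0.10 | 0.855 | 0.846 | 0.820 | 0.813 |
| 0.15 | 0.808 | 0.814 | 0.760 | 0.767 |
| 0.20 | 0.766 | 0.774 | 0.713 | 0.720 |
| 0.30 | 0.684 | 0.688 | 0.642 | 0.638 |

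When the labels are exchanged on the same draws, the two results are identical. The small gaps here (at most 0.012) are simulation noise; one estimate near 0.8 has standard error √(0.8 × 0.2 / 10,000) = 0.004. For magnitude, the exchanged run with fresh draws gives 0.81 against 0.80.

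**Step 4: is the stated 80% for breadth plausible?** Interpolating in the table, power is 0.80 at ρ of about 0.16 for 0.2 vs 1.0 and about 0.12 for 0.5 vs 1.5. The claim is therefore consistent with moderate overdispersion, but it cannot be uniquely reproduced without the HVTN 083 value.

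**The case for a change.** The strongest case for a correction is that every group-specific statement in section 6.1.2 points the wrong way and nothing else in the documents puts it right. Nor do the documents argue that gag alone should be broader on CEs. Section 4.9.3 reports gag-only breadth as 0 to 2 CEs in one place and 0 to 3 (median 0) in another, against 2 to 6 for CE prime with CE-plus-gag boost. Under the breadth scenarios as written, a significant result would in practice always favour gag alone: in 20,000 simulated runs at each correlation tried, none favoured Group 1. It is also fair that the breadth power cannot be checked exactly without the dispersion, since it runs from 0.94 down to 0.71 as the assumed correlation goes from 0 to 0.20.

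What stands is that the breadth labels are reversed and the dispersion is unstated. Three parts do not stand:

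- The trial does not lack power for its own hypothesis; Step 2 shows that the stated figure is that power.
- The magnitude sentence is not shown to be reversed. Section 4.6 aims for response levels comparable to full-length Gag, secondary objective 1 names no winner, and no section states a hypothesis that Group 1 exceeds Group 2 on magnitude. The direction of that ratio is a convention.
- The missing dispersion is a design-stage detail. The planned rank-based comparison of the arms does not use it, and printing it would not alter the 25 per arm.

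**Conclusion.** The inconsistency is real but clerical. In section 6.1.2 and the Figure 6-1 caption, the breadth scenarios attach the low mean to the CE regimen and the high mean to gag alone, against section 4.1. Exchanging the labels changes power by zero, because the arms are equal (21 evaluable each) and the test is two-sided. Sample size, allocation, significance level and the SAP analyses do not depend on which arm is named first, and the observed data will show which arm is broader. A reader who knows the schema can see what was meant.

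This conclusion rests on equal evaluable numbers in the two arms, as the plan assumes, and on the two-sided test it specifies. It does not depend on the assumed correlation: that moves the power level in both directions alike. The plotted curves in Figure 6-1 were not available, so only its caption was checked. No change to the plan follows.
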